**Figure:**

- ECG measures
  - Scatter plot and regression of  $\Delta$ QTcF on BMS-986158 concentration (with fitted line) on each study day. Scatter plots of QTcF, HR,  $\Delta$ HR on BMS-986158 concentration on each study day.

**Listing:**

- ECG measures
  - Individual QTcF, PR, QRS, HR,  $\Delta$ HR, and  $\Delta$ QTcF values will be listed.
- ECG abnormalities

## 8 CONVENTIONS

### 8.1 Date Conventions

The following conventions may be used for imputing missing or partial dates for analyses requiring dates:

AE onset date following Adverse Event Domain Requirements Specification

AE resolution/end date (these conventions may change)

- If only the day of the month is missing, the last day of the month will be used to replace the missing day. If the imputed date is after the death date or the last known alive date, then the latest known alive date or death date is considered as the resolution date.
- If the day and month are missing or a date is completely missing, it will be considered as missing

Non-study medication date following Non-Study Medication Domain Requirements Specification.

- Missing and partial radiotherapy and surgery dates will be imputed using algorithm described in APPENDIX 1.

Death date

- If only the day of the month is missing, the 1st of the month will be used to replace the missing day. The imputed date will be compared to the last known date alive and the maximum will be considered as the death date.
- If month or the year is missing, the death date will be imputed as the last known date alive.
- If the date is completely missing but the reason for death is present the death date will be imputed as the last known date alive.

Disease progression date

- If only the day of the month is missing, the 1st of the month will be used to replace the missing day
- If the day and month are missing or a date is completely missing, it will be considered as missing

- In case of the date of death is present and complete, the imputed progression date will be compared to the date of death. The minimum of the imputed progression date and date of death will be considered as the date of progression.

For other partial dates, the following conventions apply:

- If only the day of the month is missing, the 15th of the month will be used to replace the missing day
- If both the day and the month are missing, “July 1” will be used to replace the missing information
- If a date is completely missing, it will be considered as missing

The following conversion factors will be used to convert days to months or years: 1 month = 30.4375 days and 1 year = 365.25 days.

Duration (e.g. time-to onset, time-to resolution) will be calculated as follows:

$$\text{Duration} = (\text{Last date} - \text{first date} + 1)$$

Last known alive date will be defined based on all appropriate dates collected on the CRF.

All statistical analyses will be carried out using SAS (Statistical Analysis System software, SAS Institute, North Carolina, USA) unless otherwise noted.

## 8.2 Recurrent Events

In order to prepare adverse events for recurrent or multiple event analyses ([Section 7.6.6](#)), the CRF data will be processed according to standard BMS algorithms in order to collapse adverse event records into unique records based on the preferred term. This data will be presented as the rate per 100 subject-years of exposure. This analysis will take into account all on-treatment events (allowing more than 1 event per subject) and the total duration of exposure. The subject-years exposure will be computed as the sum over the subjects’ exposure expressed in years where the duration of exposure is defined as:

- Date of last dose of study treatment - date of first dose of study treatment + 100 (or 30 for monotherapy)+1 days, for subject who are off study treatment and were followed at least 100 (or 30 for monotherapy) days after last dose of study medication. Units for this calculation are subject-days.
- Last known date alive - date of first dose of study medication +1, for subjects who are still on-treatment or who are off study treatment and were followed less than 100 (or 30 for monotherapy) days after last dose of study medication. Units for this calculation are subject-days.

Subject-years are defined as the sum of subject-days divided by 365.25 and are rounded to a single decimal place of precision.

## 8.3 Pharmacokinetic Summaries

In-text Tables

For in-text pharmacokinetic tables, coefficient of variation (%CV) will be reported as integers. For other statistics except for standard deviations, values of 100 or higher will be presented as integers, values of 10 - <100 will be displayed to one decimal place, and values of 1 - < 10 will be displayed to two decimal places. Values less than 1 will be displayed to three decimal places. Ratios will also be displayed to three decimal places. Standard deviations will be reported to a precision of 1 decimal place more than the mean.

#### Handling of Non-Quantifiable Concentrations

For the summaries of concentration-time data, concentrations that are less than the lower limit of quantification (LLOQ) should be displayed as “< LLOQ” in the listings and be treated as missing in summary tables and plots. For the purpose of calculating PK parameters, other than Ctrough, pre-dose concentrations that are less than LLOQ and concentrations prior to the first quantifiable concentration that are less than LLOQ will be set to zero, and all other concentrations less than LLOQ will be set to missing.

Summary statistics for Ctrough concentrations, analyses of PD-concentrations and ECG-concentrations relationships will be calculated by imputing values less than LLOQ as  $\frac{1}{2} * \text{LLOQ}$ . This imputation is done for Ctrough concentrations because it is treated like a PK parameter; the imputation is not done for Day 1 pre-dose concentrations. Individual Ctrough listings will display these concentrations as “< LLOQ.”

All available concentration-time data and derived pharmacokinetic parameter values will be included in the PK data set and listed accordingly.

#### PK Exclusions

PK Analysis, Reporting, and Exclusion criteria should follow the BMS PK Harmonization document Version 4.0. Specific guideline for exclusionary criteria for half-life and how other PK parameters are affected for exclusion is under section 9.2 of the BMS PK Harmonization document.

Exclusion of one or more parameters or the entire dataset may be considered due to incomplete profile such as AUC(INF) or when T-HALF cannot be reliably calculated, or there is no sample around the suspected Cmax.

## **9 CONTENT OF REPORTS**

One or more interim analysis reports may be prepared. [REDACTED]

[REDACTED] No formal adjustments for multiplicity will be employed.

The clinical study report will be prepared to address the clinical objectives and endpoints identified in the protocol following closure and locking of the clinical database (CDBL).

All analyses describe in this SAP will be included in final Clinical Study Report (per data availability). Refer to the Data Presentation Plan for mock-ups of all tables and listings.

## 10 DOCUMENT HISTORY

The history of this document is as shown below in Table 10-1 below.

**Table 10-1: Document History**

Version Number	Author(s)	Description
1.0		Initial approved version
2.0		Revisions to align with revprot02-revprot07 Scope of this SAP is limited to Part 1 and Part 2 Initial expansion

## **APPENDIX 1 MISSING AND PARTIAL RADIOTHERAPY AND SURGERY DATES IMPUTATION ALGORITHMS**

### **Procedures – Imputation Rules.**

If reported procedure start date is a full valid date then set start date equal to the date part of procedure start date.

In case of partial date use imputation rules described below:

- If only day is missing then
  - If month and year of procedure match month and year of first dose date then impute as date of first dose;
  - If month and year of procedure don't match month and year of first dose date then impute as first day of that month and year.
- If both day and month are missing, then impute as maximum between 01JAN of the year and date of the first dose;
- If date is completely missing or invalid then leave missing.

Note: Imputation is not applicable to data where start date is not collected (for example "PRIOR RADIOTHERAPY" CRF). Set start date to missing in this case.

If reported end date is a full valid date then set end date equal to the date part of the reported end date.

In case of partial date use imputation rules described below:

- If reported end date is partial then set end date equal to the last possible reported end date based on the partial entered reported end date.
- If reported end date is missing, continuing, unknown or invalid then set end date equal to the most recent database extraction date.

If end date was imputed then compare end date to the death date or last known alive date if subject is not dead. If posterior then end date should be imputed to death date (or last known alive date if subject not dead).

Note: Imputation of partial dates only applies to data entered on "RADIOTHERAPY" CRF page. For other CRF pages in case of partial dates set end date to missing.

### **Surgeries – Imputation Rules.**

If reported surgery date is a full valid date then set start date equal to the date part of surgery date.

In case of partial date, use one of the two imputation rules described below:

A. For data collected on "PRIOR SURGERY RELATED TO CANCER" CRF page:

- If only day is missing then impute as the first day of the month;
- If both day and month are missing then then impute as 01JAN of the year;

- If date is completely missing or invalid then leave missing.

B. For data collected on other CRF pages (deemed to be on-treatment/subsequent surgeries):

- If only day is missing then
  - If month and year of surgery match month and year of first dose date then impute the missing date as the date of first dose;
  - If month and year of surgery don't match month and year of first dose date then impute as first day of that month and year;
- If both day and month are missing then impute as maximum between 01JAN of the year and date of the first dose;
- If date is completely missing or invalid then leave missing.

[figure not shown]

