Investigator reported CR or PR was not always confirmed by a second scan. Therefore, ORR summaries will be presented regardless of confirmation. For subjects without documented progression or subsequent therapy, all available response designations will contribute to the BOR assessment. For subjects who continue treatment beyond progression or begin subsequent therapy, the BOR should be determined based on response designations recorded up to the time of the initial RECIST v1.1 (or by Lugano 2014 criteria for hematologic malignancies, or PCWG3 criteria for prostate cancer [CRPC or NEPC]) defined progression or subsequent therapy, whichever occurs first. For those subjects who have surgical resection, only pre-surgical tumor assessments will be considered in the determination of BOR.

- Duration of Response (DOR): defined as the time between the date of first response (CR or PR) and the date of the first objectively documented disease progression (as determined using RECIST v1.1 for solid tumors, Lugano 2014 criteria for hematologic malignancies, or PCWG3 (including PSA assessments) for prostate cancer [CRPC or NEPC]), or death due to any cause, whichever occurs first. For those subjects who remain alive and have not progressed, duration of response will be censored on the date of last evaluable tumor assessment. Subjects who started subsequent therapy without a prior reported progression will be censored at the last evaluable tumor assessment prior to initiation of the subsequent anticancer therapy. Response duration will only be evaluated in subjects with a BOR of CR or PR. Duration of response will be reported if there are more than 5 CR or PR in a tumor type
- Progression Free Survival (PFS): defined as the time from the first dose of study medication to the date of the first objective documentation of tumor progression or death due to any cause. Clinical deterioration in the absence of radiographic evidence is not considered progression for the purpose of determining PFS. Subjects who neither progressed nor died will be censored on the date of their last evaluable tumor assessment. Subjects who did not have any evaluable on-study tumor assessments will be censored on the date of the first dose of study medication. Subjects who started subsequent therapy without a prior reported progression will be censored at the last evaluable tumor assessment prior to initiation of the subsequent anticancer therapy.

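### A surgery known only by its year can be dated at first dose, which removes every on-study scan from that subject's best overall response

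*SAP*

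**What the plan says.** SAP Section 8.1 opens by saying that its date conventions may be used, but on this item it is directive: "Missing and partial radiotherapy and surgery dates will be imputed using algorithm described in APPENDIX 1".

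Appendix 1 sorts surgeries by CRF page. Rule A covers prior cancer surgery. Rule B covers all other pages, whose entries are treated as on-treatment or later:

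- Day missing, month of first dose: "If month and year of surgery match month and year of first dose date then impute the missing date as the date of first dose".
- Day missing, any other month: "then impute as first day of that month and year".
- Day and month missing: "If both day and month are missing then impute as maximum between 01JAN of the year and date of the first dose".
- No date: left missing.

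Radiotherapy start dates, under the Procedures rules of the same appendix, follow the same pattern: "If both day and month are missing, then impute as maximum between 01JAN of the year and date of the first dose" and "If date is completely missing or invalid then leave missing".

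The results feed Section 4.2.1. The BOR window closes at first documented progression or subsequent therapy. After resection, "only pre-surgical tumor assessments will be considered in the determination of BOR". PFS and DOR are censored at the last evaluable scan before subsequent anticancer therapy. PFS is censored at first dose if there is no evaluable on-study scan.

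Section 7.5 bases the final efficacy analysis on All Treated. For progression dates, Section 8.1 replaces a missing day with the 1st of the month and treats a date without a month as missing. The only bound on the imputed date is at death: "The minimum of the imputed progression date and date of death will be considered as the date of progression".

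**The concern.** The surgery rule picks the earliest date compatible with the record, limited only by first dose. It is not checked against last dose or the last tumor assessment. Elsewhere the SAP does bound imputed dates: an imputed death date cannot precede the last date known alive, and an imputed radiotherapy end date cannot pass death or last known alive.

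Combined with the pre-surgical rule for BOR, the result is perverse. A site that knows the year of a resection can cost the subject every on-study scan, while a site that knows nothing costs the subject none. With 5 to 9 subjects per expansion cohort, one lost responder is visible in the reported ORR.

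**Working it through.** **No stated figure to reproduce.** The documents give no number for this rule. As a check that I read the two-stage boundaries correctly, I recomputed the error rates in SAP Table 5.2-1, counting 2 or more of 5 responses at Stage 1 as a signal.

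- Cohorts at 10% versus 50%, boundaries 0/2 then 2/3: FPR = P(X1≥2) + P(X1=1)·P(X2≥2) = 0.0815 + 0.3281 × 0.0523 = 9.9%. FNR is 8.0%. The table states 10/10.
- Cohorts at 10% versus 35%, boundaries 0/2 then 1/2: FPR 19.4%, FNR 17.2%. The table states 20/20.

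Both agree if the table's figures are upper limits.

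**One subject, dates assumed.** The dates fall after 18-Mar-2019 because Revised Protocol 07 defined the Initial Expansion.

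- First dose 15-Apr-2019; PR on 10-Jun and 05-Aug; progression and last dose 02-Dec-2019. A later resection is recorded only as 2019.
- Rule B: max(01-Jan-2019, 15-Apr-2019) = 15-Apr-2019.
- On-study scans before 15-Apr-2019: none. The PR is lost and BOR is not evaluable.
- With no date recorded, nothing is cut and BOR = PR.
- With a floor at last dose + 1, the surgery is dated 03-Dec-2019, still within 2019, and BOR = PR.

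**Effect on a cohort of nine, All Treated denominator.**

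- 3/9 = 33.3% (95% Clopper-Pearson 7.5 to 70.1) becomes 2/9 = 22.2% (2.8 to 60.0), a drop of 1/9 = 11.1 points.
- For NMC, DHL and TNBC the Stage 2 boundary is 2/3, so 3/9 meets it and 2/9 does not. For non-GC-DLBCL and CRPC (1/2) the corresponding step is 2/9 to 1/9.

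**Which year-only dates are affected.** Suppose first doses are spread evenly over a 365-day year and the true surgery is L days after first dose. The imputed date equals first dose when both fall in one calendar year, a share of (365 − L)/365. It falls on or before the day-56 scan in (365 − L + 56)/365, for L of at least 56.

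| True surgery, days after first dose | Imputed to first dose | On or before day-56 scan |
|---|---|---|
| 63 | 302/365 = 83% | 358/365 = 98% |
| 119 | 246/365 = 67% | 302/365 = 83% |
| 189 | 176/365 = 48% | 232/365 = 64% |
| 287 | 78/365 = 21% | 134/365 = 37% |
| 364 | 1/365 = 0% | 57/365 = 16% |

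These shares are conditional on a year-only date having been recorded.

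**Day-missing surgery dates.** The shift is at most 30 days. In the month of first dose no scheduled scan has yet occurred. In a later month only a scan in that same month can be lost: the day-56 scan in 77% of cases for a true surgery on day 63, 31% on day 77, and none from day 119.

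**Day-missing progression dates.** The shift is again at most 30 days. Part 2 scans are every 8 weeks ± 1 week, so the first two are at least (112 − 7) − (56 + 7) = 42 days apart. An imputed progression at the second scan therefore stays at least 42 − 30 = 12 days after the first. Enumeration over four years of first-dose dates found 0 of 328,500 combinations in which it reached a response at the first scan. Progression at the earliest first scan still gives PFS of at least 49 − 30 + 1 = 20 days. A second-scan progression moved to within week 12 in 8.8% of combinations.

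**The case against.** The best defence is that earliest-possible imputation limited by first dose is a stated convention, and Section 8.1 calls its conventions optional. The harm also needs a coincidence: a responder who is resected, with a date known only to the year, in the year of first dose. The two-stage boundaries only guide assessment, the sponsor decides on the whole of the accruing evidence (SAP Section 2.1), and there is no formal hypothesis. The pre-surgical rule itself is sound, because a resected target lesion would otherwise register as shrinkage.

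Most of this stands and limits the importance of the point. It does not rescue the rule, which still treats a partly known date worse than an unknown one and can misstate ORR.

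A reader might go further in four ways that the documents do not support:

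- *Any partial surgery date goes to first dose.* This holds only if the year matches (year-only date) or the month and year match (day missing).
- *A partial progression date can erase a response.* Year-only progression dates are set to missing, and planned scan spacing exceeds the largest shift. Only an unscheduled scan could do it.
- *PFS and DOR are cut at the imputed surgery date, and radiotherapy does the same to all three endpoints.* This needs surgery or radiotherapy to count as subsequent therapy. The SAP never says so, and its resection rule does not mention radiotherapy. Protocol Section 3.4 allows limited-field palliative radiation on study.
- *One such date decides a cohort.* It can move a cohort across a guiding boundary, but no decision follows automatically.

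**Conclusion.** The point holds for one combination: a resection recorded as on-treatment or subsequent, dated only by year, in the year of first dose. Appendix 1 then places it at first dose, and Section 4.2.1 leaves no on-study scan for BOR. The cost is 11 points of ORR per affected responder in a cohort of nine, enough to take 3/9 to 2/9.

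This assumes that the imputed date is the one used to apply the pre-surgical rule, as the directive sentence in Section 8.1 implies. The frequency of year-only dates is not given and is assumed rare, so no expected effect can be calculated. Effects on PFS or DOR, and any effect of radiotherapy, remain conditional on an undefined term. This is a low-priority gap in specification, worth closing because the cohorts are small and the repair is cheap.

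**What to change.** In SAP Appendix 1:

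- For surgery and radiotherapy known to follow the end of treatment, use the later of the current imputed date and last dose date + 1, kept within the reported month or year.
- For on-treatment resections with a year-only date, query the site. If the date stays unresolved, keep the pre-surgical rule and show ORR with and without the exclusion as a sensitivity analysis. Dropping the rule altogether would let post-resection scans count as response.

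In SAP Section 4.2.1, state whether surgery and radiotherapy, including permitted palliative radiation, count as subsequent anticancer therapy for BOR, DOR and PFS.

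As a minor consistency point in SAP Section 8.1, set a day-missing progression date no earlier than the day after the last evaluable assessment without progression, still capped at death. This floor would bind only for unscheduled scans.

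The cost is SAP wording, minor programming and possibly a few site queries, with no new data collection.
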